## PROTOCOL SYNOPSIS

Title of Study	A Multi-Center, Open-Label, Randomized Phase 1/2 Study of Copper Cu 64 PSMA I&T Injection in Patients with Histologically Proven Metastatic Prostate Cancer
Phase of Clinical Trial	Phase 1/2
Indication	Detection and localization of recurrent prostate cancer in men with biochemical recurrence based on elevated blood prostate specific antigen (PSA) levels following prior treatment.
Number of Sites	5-10
Drug Product	Copper Cu 64 PSMA I&T
Study Objectives	
Phase 1
 
Primary Objectives:
 
The primary objectives of the Phase 1 portion of this study are:
 

1. To assess the safety and determine radiation dosimetry estimates following intravenous administration of 5, 7, and 9 mCi doses of copper Cu 64 PSMA I&T injection in patients with recurrent prostate cancer. Safety will be assessed by monitoring adverse events, clinical chemistry, hematology, urinalysis, vital signs, ECG, and determination of radiation absorbed dose estimates.

2. To assess the PET/CT image quality following intravenous administration of 5, 7, and 9 mCi doses of copper Cu 64 PSMA I&T injection to determine an acceptable dose for obtaining diagnostic quality PET/CT images.

 
Phase 2
 
Primary Objectives:
 
The primary objectives of the Phase 2 portion of this study are:
 

1. To determine the region-level correct localization rate (CLR) of copper Cu 64 PSMA I&T injection PET/CT imaging for the detection of recurrent metastatic prostate cancer at 1 hour and 4 hours post injection. The CLR is defined as the percentage of regions containing at least one true PET positive lesion, with exactly localized correspondence between PET/CT imaging and the Composite Reference Standard regardless of any co-existent false positive findings, within the same region, out of all regions containing at least one PET positive finding.

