	
2. To determine the patient-level correct detection rate (CDR) of copper Cu 64 PSMA I&T injection PET/CT imaging for the detection of recurrent metastatic prostate cancer at 1 hour and 4 hours post injection. The CDR is defined as the percentage of patients who have at least one true PET positive lesion, with exactly localized correspondence between PET imaging and the Composite Reference Standard, regardless of any co-existent false positive findings, out of all patients who are scanned.
 
3. To assess the safety of copper Cu 64 PSMA I&T injection in patients with recurrent prostate cancer. Safety will be assessed by monitoring adverse events, clinical chemistry, hematology, urinalysis, ECG, and vital signs.
 
Secondary Objective:
 
1. To compare the diagnostic quality of PET/CT images obtained at 1 hour and 4 hours post copper Cu 64 PSMA I&T injection.

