Study Population	
The study will include patients with metastatic proven prostate adenocarcinoma.
 
Phase 1: Total of 12 patients.
 
Inclusion Criteria:
 

1. Patients with histologically proven prostate adenocarcinoma.

2. Prior radical prostatectomy or radiation therapy with curative intent.

3. Recurrence of disease, defined as:

a. Prior Radical Prostatectomy: PSA > 0.2 ng/mL, or

b. Prior Radiation Therapy: 2 ng/mL rise in PSA over post-treatment nadir.

4. Patients with at least one extraprostatic site of disease suspected based on prior imaging or diagnosed by biopsy.

5. Age greater than or equal to 18 years.

6. Able to understand and provide signed written informed consent.

 
Exclusion Criteria:
 

1. Body weight greater than 350 lb. (158 kg).

2. Investigational therapy within the past 30 days.

3. Creatinine clearance (ClCr) less than 30 mL/min.

4. Participants who are capable of fathering a child and who are unwilling to take precautions to prevent pregnancy.

 
Phase 2: Total of 26 patients.
 
Inclusion Criteria:
 

1. Patients with histologically proven prostate adenocarcinoma.

2. Prior radical prostatectomy or radiation therapy with curative intent.

3. Recurrence of disease defined as:

a. Prior Radical Prostatectomy: PSA > 0.2 ng/mL, or

	
b. Prior Radiation Therapy: 2 ng/mL rise in PSA over post-treatment nadir
 
4. Patients with at least one extraprostatic site of disease suspected based on prior imaging or diagnosed by biopsy.
 
5. Age greater than or equal to 18 years.
 
6. Able to understand and provide signed written informed consent.
 
Exclusion Criteria:
 

1. Androgen deprivation therapy (ADT) or other therapies targeting the androgen pathway unless subject has a rising PSA level.

2. Body weight greater than 350 lb (158 kg).

3. Investigational therapy within the past 30 days.

4. Creatinine clearance (ClCr) less than 30 mL/min.

5. Participants who are capable of fathering a child and who are unwilling to take precautions to prevent pregnancy.

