	
Baseline Assessments:
 
Routine clinical chemistry, hematology, and urinalysis will be obtained for all patients prior to dosing. PSA will also be obtained for all patients prior to dosing.
 
Medical history and physical examination will be performed prior to dosing. This will include information on the history of the prostate cancer. Concomitant medication history will also be obtained.
 
Imaging Procedure:
 
All patients will undergo PET/CT imaging at 1 hour <math>\pm</math> 15 minutes and 4 hours <math>\pm</math> 30 minutes following copper Cu 64 PSMA I&T injection using the dose determined in Phase 1. The 1 hour and 4-hour images will be independently read by three experienced blinded readers for the detection of prostate cancer. Specifically, each reader will categorize images as “Disease” or “No Disease” based only on tumor uptake of copper Cu 64 PSMA-I&T in each of the four regions: 1) prostate bed or prostate gland, 2) lymph nodes (pelvic and extra pelvic), 3) bone, and 4) viscera/soft tissue.
 
Efficacy Analysis:
 
Composite Reference Standard
 
All patients will undergo an efficacy assessment based on copper Cu 64 PSMA I&T PET/CT results and the results of clinical presentation for evaluation against the Composite Reference Standard.
 
The Composite Reference Standard is defined as follows:
 

1. Local histopathology obtained from prostate cancer surgery or biopsy obtained within 60 days before or following copper Cu 64 PSMA I&T PET/CT, or

2. If histopathology is not available, anatomical correlation of conventional image findings (e.g., targeted MRI or CT or any FDA-approved PET PSMA agent) that are acquired prior to locoregional or systemic treatment and within 60 days before or following copper Cu 64 PSMA I&T PET/CT

 
Safety Assessments:
 
All patients will be followed for adverse events for 24 hours post-injection. Severity of adverse events will be assessed independently by the Investigators and graded using the National Cancer Institute Common Terminology Criteria for Adverse Events version 5.0, in which Grades 1, 2, 3, 4, and 5 describe adverse events as mild, moderate, severe or medically significant but not life-threatening, life-threatening, and death related to the adverse event, respectively.

--	---

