	
1. To determine the region-level correct localization rate (CLR) of copper Cu 64 PSMA I&T injection PET/CT imaging for the detection of recurrent metastatic prostate cancer at 1- and 4-hours post-injection. The CLR is defined as the percentage of regions containing at least one true PET positive lesion, with exactly localized correspondence between PET/CT imaging and the Composite Reference Standard regardless of any co-existent false positive findings, within the same region, out of all regions containing at least one PET positive finding.
 
2. To determine the patient-level correct detection rate (CDR) of copper Cu 64 PSMA I&T injection PET/CT imaging for the detection of recurrent metastatic prostate cancer at 1 hour and 4 hours post-injection. The CDR is defined as the percentage of patients who have a least one true PET positive lesion with exactly localized correspondence between PET imaging and the Composite Reference Standard regardless of any co-existent false positive findings, out of all patients who are scanned
 
Since all patients enrolled in the study will have disease, the CLR is a measure of the sensitivity of the copper Cu 64 PSMA I&T injection scan. Current methods have a CLR of 60%; thus, the hypothesis to be tested in the Phase 2 portion of the study is: H0: <math>\pi_C = \pi_0</math> versus HA: <math>\pi_C > \pi_0</math> where <math>\pi_C</math> is the CLR for copper Cu 64 PSMA I&T injection and <math>\pi_0</math> is the CLR from the literature (estimated to be 60%).
 
This hypothesis will be tested using an exact one-sample binomial test with a one-sided <math>\alpha=0.025</math>.
 
Secondary Objective:
 
The secondary objective for the Phase 2 study is to compare the diagnostic quality of PET/CT images obtained at 1 hour and 4 hours post copper Cu 64 PSMA I&T injection.
 
Safety Endpoint:
 
To assess the safety of copper Cu 64 PSMA I&T injection in patients with recurrent prostate cancer. Safety will be assessed by monitoring adverse events, clinical chemistry, hematology, urinalysis, ECG, and vital signs.
 
Analysis Populations:
 
Several analysis populations of patients are defined, which may provide a more complete description of the collected data, provide a logical mechanism for grouping and listing results based on an applied analysis, and/or allow appropriate stratification of various analyses.
 
1. The Enrolled Patient Population (EPP) represents patients who sign an Informed Consent Form and have baseline data.

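### The plan calls the CLR a measure of sensitivity, but its denominator is PET-positive regions, so rejecting the 60% null does not show sensitivity above 60%

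*Combined protocol and SAP*

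**What the plan says.** The Phase 2 primary objectives and the Primary Efficacy Endpoints (Protocol Synopsis, Study Objectives and Statistical Analysis) define two rates.

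- **CLR (region level).** "The CLR is defined as the percentage of regions containing at least one true PET positive lesion", matched in location to the Composite Reference Standard, "out of all regions containing at least one PET positive finding".
- **CDR (patient level).** Patients with at least one correctly localized true-positive lesion, "out of all patients who are scanned".

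Directly after these definitions the Statistical Analysis section interprets the CLR: "Since all patients enrolled in the study will have disease, the CLR is a measure of the sensitivity of the copper Cu 64" PSMA I&T scan. It then sets H0: CLR = 60% against a one-sided alternative, taking the 60% as a CLR from the literature. "This hypothesis will be tested using an exact one-sample binomial test", at one-sided alpha 0.025. This is the only hypothesis test in the synopsis.

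Two further passages bear on the point. Phase 2 inclusion criterion 4 reads: "Patients with at least one extraprostatic site of disease suspected based on prior imaging or diagnosed by biopsy". The Composite Reference Standard falls back on imaging: "If histopathology is not available, anatomical correlation of conventional image findings".

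**The concern.** Sensitivity divides by diseased units. The CLR divides by PET-positive units. The stated reason, that every enrolled man has disease, is a condition on patients. It does not make each of a man's four regions diseased, and it does not bring PET-negative regions into the denominator. Criterion 4 also admits men whose extraprostatic site is only suspected, although this is secondary: the mismatch would remain if every man had proven disease.

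What is at stake is the meaning of a positive result. The sentence introduces the test, so it tells the reader what a rejected H0 shows. A tracer that is rarely wrong when it lights up, but often fails to light up, could pass and then be described as having sensitivity above 60%.

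**Working it through.** **Inputs from the synopsis.** 26 Phase 2 men; four regions per man (prostate bed or gland, lymph nodes, bone, viscera/soft tissue); null value 60%; exact one-sample binomial test, one-sided alpha 0.025. The synopsis gives no sensitivity figure to reproduce.

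**Assumptions.** D, the number of diseased regions among the 26 men, is not given. I use 26, 39 and 52 (1, 1.5 and 2 per man). The true-positive (TP) and false-positive (FP) counts are illustrative. Regions are treated as independent in the test.

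**Formulas, by region (FN = false negative)**

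- CLR = TP / (TP + FP). This holds if every PET-positive region has a reference result or unverified ones count as false; the Composite Reference Standard text does not settle this.
- Sensitivity = TP / (TP + FN) = TP / D.

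FN does not appear in the CLR. With TP > 0, the two rates are equal only when FP = FN.

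**Test.** p = P(X ≥ TP), with X binomial on TP + FP regions and success probability 0.60. For 8 of 8 this is 0.6^8 = 0.0168. CDR intervals are exact (Clopper-Pearson) 95%.

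| Case | TP, FP | CLR | p | CDR (95% CI) | Sensitivity at D = 26 / 39 / 52 |
|---|---|---|---|---|---|
| a | 16, 2 | 16/18 = 88.9% | 0.0082 | at most 16/26 = 61.5% (40.6% to 79.8%) | 61.5% / 41.0% / 30.8% |
| b | 8, 0 | 8/8 = 100% | 0.0168 | at most 8/26 = 30.8% (14.3% to 51.8%) | 30.8% / 20.5% / 15.4% |
| c | 26, 2 (one true region per man) | 26/28 = 92.9% | 0.00012 | 26/26 = 100% (86.8% to 100%) | 100% / 66.7% / 50.0% |

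The CDR in cases a and b is an upper limit, because 16 or 8 true regions can lie in at most 16 or 8 men.

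All three cases reject H0. In a and b the CDR gives warning. In c it does not: each man has one region found, and the missed regions affect neither endpoint.

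**The reverse also occurs.** With D = 40, TP = 36, FN = 4 and FP = 30, sensitivity is 36/40 = 90%, but the CLR is 36/66 = 54.5% (p = 0.85), so H0 is not rejected. The CLR therefore bounds sensitivity in neither direction.

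**The case against.** The strongest reply is that the plan never says a rejection demonstrates sensitivity above 60%. Both sides of the hypothesis are defined as CLRs, so the test is valid for what it tests, and the error is confined to one explanatory sentence. The co-primary CDR counts every scanned man and would expose cases a and b. Case c needs a particular pattern, D is assumed, and some table entries (61.5%, 66.7%, 100%) lie above 60% anyway. Histological proof of cancer and biochemical recurrence are also entry criteria, so disease at patient level has more support than criterion 4 alone suggests. Nothing in the synopsis indicates that the 60% follows a different definition.

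Most of this stands. The test is coherent, the CDR is a partial safeguard, and the examples show that the rates can diverge, not how far they will in this trial. Checking the 60% is prudence, not correction of a demonstrated error. Using the CDR for detection statements does not make regionally missed disease visible.

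None of it rescues the sentence. A primary endpoint labelled a measure of sensitivity and then tested against 60% invites the wrong reading, and better evidence of patient-level disease leaves the CLR denominator unchanged.

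**Conclusion.** The concern holds. As defined, the CLR is a PPV-type rate among PET-positive regions and cannot measure sensitivity. This follows from the definition alone and depends on none of the assumed counts. Rejecting H0 supports a CLR above 60% and nothing about the share of diseased regions found.

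The possible gap is large: an observed CLR of 88.9% that passes the test is compatible with region sensitivity from 61.5% down to 30.8% over the assumed range of D, and a CDR of 100% is compatible with 50.0% at D = 52. These are illustrations, not estimates for this trial.

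This should be fixed because the sentence governs the interpretation of the only tested endpoint in the synopsis. The hypothesis test itself is not at fault.

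**What to change.** 1. Replace the sentence with: *The CLR is a region-level, PPV-type rate among PET-positive regions; it does not measure sensitivity.* Report a rejected H0 only as a CLR above 60%. This is the essential change.
2. Confirm that the literature figure of 60% was computed as correctly localized regions out of PET-positive regions, and restate it if it was not.
3. Base statements about detection on the CDR with an exact 95% confidence interval, described as a patient-level rate that does not count regions missed in a man with another correct region.

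The cost is one sentence, one check of a source, and exact intervals on an endpoint already planned. Data collection, the CLR denominator, alpha and the test stay as they are; the null value changes only if step 2 requires it. What the sponsor gives up is the ability to describe the CLR result as sensitivity.

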Study Design	
This is a prospective, open-label Phase 1/2 study to evaluate copper Cu 64 PSMA I&T injection for PET/CT imaging in patients with recurrent metastatic prostate cancer after radical prostatectomy or radiation therapy.
 
Phase 1
 
The Phase 1 portion of the study will include a total of 12 patients with metastatic prostate cancer. Patients will be randomized into three groups of four patients. Patients in each group will receive a single intravenous dose of 5, 7, or 9 mCi of copper Cu 64 PSMA I&T. Whole-body PET/CT images will be acquired at 1 hour <math>\pm</math> 15 minutes, 4 hours <math>\pm</math> 0.5 hours, and 24 hours <math>\pm</math> 2.0 hours post-injection to determine radiation absorbed dose estimates.
 
The 1 hour and 4-hour PET/CT images will be evaluated independently by three readers blinded to all patient information and dose administered to assess the quality of the images (24 PET/CT image sets total). The assessments will be used to determine an acceptable dose to be administered for the Phase 2 study.
 
Phase 2
 
The Phase 2 portion of the study will include a separate group of 26 patients with metastatic prostate cancer. Each patient will be administered the same intravenous dose of copper Cu 64 PSMA I&T injection determined in the Phase 1 study. PET/CT images will be acquired for all patients at 1 hour <math>\pm</math> 15 minutes and 4 hours <math>\pm</math> 30 minutes post copper Cu 64 PSMA I&T injection.
 
The PET/CT images will be interpreted independently by three readers blinded to all patient information. Each patient study will be assessed and scored for the detection of prostate cancer. Specifically, each reader will categorize images as "Disease" or "No Disease" based only on tumor

	
uptake of copper Cu 64 PSMA-I&T in each of the four regions: 1) prostate bed or prostate gland, 2) lymph nodes (pelvic and extra pelvic), 3) bone, and 4) viscera/soft tissue. Analysis of the reads will be used for determination of the CLR and CDR for 1 hour and 4-hour post-injection imaging of copper Cu 64 PSMA I&T PET/CT by comparison to the Composite Reference Standard.

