Phase 2 Study Procedures	
A total of 26 patients will be included in the Phase 2 portion of the study.
 
Screening:
 
All patients will be screened to ensure they meet all inclusion and no exclusion criteria for enrollment in the study. Written informed consent will be obtained for all patients enrolled in the study.

---------------------------------	---

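### The exact binomial test of the region-level CLR treats regions from the same patient as independent, so the one-sided 0.025 level is not assured

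*Combined protocol and SAP*

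**What the plan says.** All references are to the Protocol Synopsis, the only part of the plan supplied.

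- **Unit of analysis.** Under Primary Efficacy Endpoints, the CLR is a percentage of regions, "out of all regions containing at least one PET positive finding". The patient-level correct detection rate (CDR) is instead taken "out of all patients who are scanned".
- **Regions per patient.** Under Study Design, Phase 2, readers classify disease "in each of the four regions: 1) prostate bed or prostate gland", lymph nodes, bone, and viscera/soft tissue. One patient can therefore add up to four regions to the CLR denominator. A patient read negative everywhere adds none, but still counts for the CDR.
- **Number of patients.** "A total of 26 patients will be included in the Phase 2 portion of the study". Inclusion criterion 4 sets a minimum of one suspected or biopsy-diagnosed extraprostatic site and no maximum.
- **Test.** The CLR is tested against a literature value of 60%: "This hypothesis will be tested using an exact one-sample binomial test with a one-sided" level of 0.025.

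No clustered method, design effect or within-patient correlation appears. The only sample size text concerns Phase 1.

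**The concern.** An exact binomial test is exact only for independent trials with a common success probability. A patient's regions share the injection, the scan and, within a read, the reader. They may also share the quality of verification, because the Composite Reference Standard is histopathology for some patients and conventional imaging for others. Regions in one patient may therefore be confirmed or missed together. This is a plausible mechanism, not a measured correlation.

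Positive correlation makes the total number of correct regions more variable than the binomial allows, while the rejection cut-off stays where the binomial puts it. The trial could then declare a CLR above 60% more often than the stated 2.5% when the true CLR is 60%. This is a primary endpoint with a formal hypothesis, so the level matters.

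**Working it through.** **Inputs from the synopsis:** 26 patients, at most four regions each, null CLR 0.60, one-sided level 0.025.

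**Assumed, because the documents do not give them:** the number of PET-positive regions per patient, and the ICC.

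**Step 1. The stated test with independent regions.** For n regions the cut-off is the smallest r with P(X ≥ r) ≤ 0.025, where X ~ Binomial(n, 0.60).

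| Regions per patient | n | r | Attained size |
|---|---|---|---|
| 1 | 26 | 21 | 0.0214 |
| 2 | 52 | 39 | 0.0173 |
| 3 | 78 | 56 | 0.0205 |
| 4 | 104 | 73 | 0.0202 |

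The level holds, with some slack because the counts are discrete.

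**Step 2. Same cut-offs, regions correlated within patient.** Each patient's count is beta-binomial with mean 0.60 and correlation ρ. Convolving the 26 patients gives the exact distribution of the total.

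| Regions per patient | ρ = 0.1 | ρ = 0.2 | ρ = 0.3 | ρ = 0.5 |
|---|---|---|---|---|
| 1 | 0.0214 | 0.0214 | 0.0214 | 0.0214 |
| 2 | 0.0220 | 0.0270 | 0.0322 | 0.0431 |
| 3 | 0.0311 | 0.0424 | 0.0538 | 0.0758 |
| 4 | 0.0362 | 0.0530 | 0.0695 | 0.0997 |
| Mix (13, 8, 4, 1 patients with 1, 2, 3, 4 regions; n = 45, r = 34) | 0.0278 | 0.0343 | 0.0410 | 0.0546 |

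Hand check for three regions and ρ = 0.3: the variance inflation is 1 + (3 − 1) × 0.3 = 1.6. The null mean is 78 × 0.6 = 46.8 and the inflated SD is √(78 × 0.24 × 1.6) = 5.47. With a continuity correction, z = (55.5 − 46.8)/5.47 = 1.59, a tail of about 0.056. The exact value is 0.0538.

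**Step 3. Region counts varying at random between patients.** Beta-binomial simulation, 300,000 trials per cell. Assumed probabilities of 1, 2, 3 and 4 regions among contributing patients are (.80, .17, .02, .01), (.62, .28, .08, .02), (.40, .35, .20, .05), (.25, .35, .25, .15) and (.05, .25, .35, .35).

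| Mean regions | ICC 0.1 | ICC 0.3 | ICC 0.5 | ICC at which size passes 0.025 |
|---|---|---|---|---|
| 1.24 | 0.019 | 0.024 | 0.027 | about 0.38 |
| 1.5 | 0.019 | 0.027 | 0.036 | about 0.24 |
| 1.9 | 0.023 | 0.036 | 0.050 | about 0.12 |
| 2.3 | 0.026 | 0.044 | 0.063 | about 0.09 |
| 3.0 | 0.030 | 0.054 | 0.078 | about 0.06 |

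Four regions in every patient is an upper bound; its exact sizes are in Step 2. If 15% of patients contribute no region, the sizes change by at most 0.002; with 30%, by at most 0.005.

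**Step 4. A patient-clustered alternative.** Let m_i be the PET-positive regions and x_i the correct ones in patient i. The score statistic is T = Σ(x_i − 0.6 m_i) / √Σ(x_i − 0.6 m_i)², summed over patients with m_i ≥ 1 and referred to t with (number of such patients − 1) degrees of freedom. Over ICC 0 to 0.5 and all the region distributions, including four regions in every patient, its simulated size is 0.021–0.027 when every patient contributes, 0.020–0.026 with 15% contributing none, and 0.019–0.025 with 30%. The denominator cannot be zero, because 0.6m is 0.6, 1.2, 1.8 or 2.4, never a whole number.

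**The case against.** **The inflation rests on assumed inputs.** This is true. With one positive region per patient there is none, and at a mean of 1.24 or 1.5 the ICC must exceed about 0.38 or 0.24. The largest figures need every patient positive in all four regions. But at a mean of 1.9 an ICC of about 0.12 is enough, and nothing supplied excludes that.

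**The error can run the other way.** With a negative within-patient correlation of −0.2 and two regions per patient, the size is 0.0094. Regions with different success rates and no patient effect also make the pooled test conservative: about 0.013–0.014 with assumed rates of 0.35, 0.85, 0.70 and 0.50 and all four regions positive. This stands, and is why the claim is only that the level is not assured. In that second case the clustered test, at 0.020, is closer to nominal.

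**The replacement is approximate.** Its size reaches 0.027, and at a mean of 1.24 regions with ICC 0 it is larger than that of the stated test (0.0255 against 0.0178). This stands and should be disclosed. The excess is about 0.002, against 0.02 or more for the stated test in several plausible cells.

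**Other sections may adjust.** Only the synopsis was available. Any adjustment elsewhere would still have to be reconciled with the specific test named here.

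**Conclusion.** The concern holds. The synopsis applies a test for independent observations to a rate whose units are grouped within patients, and supplies no adjustment. Under positive correlation, with a mean of 1.9 to 3.0 regions per contributing patient and an ICC of 0.3, the one-sided size is about 0.036 to 0.054 instead of 0.025. The level is kept if there are few regions per patient or the ICC is low. Confidence is high that the supplied text lacks an adjustment. No particular amount of inflation can be asserted, because the ICC and region counts are assumptions. This should be fixed before the CLR is tested.

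**What to change.** In the Phase 2 hypothesis test, replace the exact binomial test of the CLR with the patient-clustered score test in Step 4, at one-sided 0.025. State that its small-sample size is approximate, up to about 0.027 in simulation. Keep the exact binomial method for the CDR, which has one observation per patient.

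Do not invert this statistic to get a confidence interval. If a CLR interval is reported, use a patient-clustered method whose lower-limit coverage has been checked by simulation with 26 patients at CLRs of 80–95%.

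Apply the test to each reader separately; do not pool the three reads as independent observations. The success rule across readers and across the 1-hour and 4-hour images is a separate matter that this change does not settle.

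**Cost.** Statistical wording only, with no added patients or procedures, but a real loss of power. At an assumed true CLR of 80% and ICC 0.3 (60,000 simulated trials per cell):

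| Mean regions | All contribute: stated → clustered | 15% contribute none: stated → clustered |
|---|---|---|
| 1.5 | 70% → 67% | 63% → 59% |
| 1.9 | 80% → 72% | 73% → 64% |
| 2.3 | 86% → 76% | 80% → 67% |

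Part of each gap is only the stated test's excess size. The sponsor should recheck that 26 patients are enough under its own planning CLR, which the supplied text does not give.
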